#### **1** Introduction

This document describes additions and changes to the Final Version 1.0 of the Statistical Analysis Plan (SAP) for Protocol NEU-2591-PTHS-001. The section numbers following the introduction in this document correspond to those updated from the SAP Final Version 1.0; therefore, they are not sequential. The reader is referred to SAP Final Version 1.0 for analysis descriptions for sections that are not included in this document.

#### **5.3 Definitions**

• Number of missed doses will be derived based on the number of expected doses – the number of doses taken. If a subject took more doses than expected, the number of missed doses will be taken to be 0.

The reader is referred to Section 5.3 of the SAP Final Version 1.0 for other analysis definitions.

#### 9.2.10 Behavior Problems Inventory-Short Form

The BPI-SF will be completed at Visit 3 (Week 0) and at the End of Treatment (Week 13, Visit 16). The BPI-SF is a caregiver-completed rating scale for assessing self-injury, aggressive and stereotyped behavior. Each item is measured for frequency and items in the Self-Injurious Behavior and Aggressive/Destructive Behavior subscales are also assessed for severity. The frequency is scored on a 5-point scale, where 0=never/no problem; 1=monthly, 2=weekly, 3=daily, 4=hourly. The severity is scored on a 3-point scale, where 1=mild, 2=moderate, 3=severe. The items are grouped in three subscales: Self-Injurious Behavior (score ranges from 0 - 32 for frequency and 8 - 24 for severity), Aggressive/Destructive Behavior (score ranges from 0 - 40 for frequency and 10 - 30 for severity), and Stereotyped Behavior (score ranges from 0 - 48 for frequency). The score for each subscale is the sum of the items within that domain. The total frequency score is the sum of the frequency scores for the three domains. The total severity score is the sum of the severity scores for Aggressive/Destructive Behavior and Self-Injurious Behavior subscales. The total severity and frequency scores will only be calculated if all contributing domain scores are not missing. Missing items will be imputed as defined in Section 5.2.5. A subscale score will only be calculated if all items in that domain are answered or can be imputed. Lower scores indicate lesser frequency and severity in behavior problems. Within subject change is the difference between the score at EOT and the score at baseline.

Summary statistics for the total score, subscale scores and their changes from baseline in the frequency and severity of BPI-SF scores will be displayed at End of Treatment. Within subject changes will be analyzed using a Wilcoxon signed rank test. The change from baseline in the total frequency and severity scores at EOT will be presented in plots as described in Section 9.2. The change from baseline in the subscale scores at EOT will be presented in a forest plot and waterfall plots. The subscale and total scores will be presented in line graphs at each visit.

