Seizures present another challenge for 30%-51% of individuals with PTHS. ^{4, 6, 8-11, 13, 15} The range of seizure types includes generalized tonic-clonic, atonic, focal onset, and infantile spasms. ^{6, 8, 10, 16-18} Additionally, between 18%-42% of individuals with PTHS experience some type of sleep disturbance, typically insomnia or night awakenings. ^{6, 8}

Individuals with PTHS face a range of behavioral challenges.^{3, 4, 6-8, 10} Compared to Angelman Syndrome (AS) and Cornelia de Lange syndrome (CdLS), other genetically based disorders with similar early signs and features, the behavioral phenotype of PTHS is particularly characterized by the following: 1) a high level of Autism Spectrum Disorder (ASD) symptomatology 2) social communication difficulties, 3) atypical sensory processing, and 4) high levels of physical aggression and self-injury.¹³ Aggression and aggressive behavior are observed in 40%-54% of individuals,^{8, 11-13} and in 38% of individuals, this has included destruction of property.¹³ Between 60-71% of individuals demonstrate self-injurious behaviors.^{6, 9, 11} Anxiety (81%) and agitation (88%) are also common symptoms.⁶

Up to 95% of individuals met the cut off score for possible ASD on the Social Communication Questionnaire (SCQ) screener for ASD. ¹³ Individuals have also been shown to score high on the Autism Diagnostic Interview measure. ¹² On the SCQ, they demonstrated more problems with communication and reciprocal social interaction than individuals with AS. They also showed lower sociability with both

familiar and unfamiliar people compared to individuals with AS, and with familiar people compared to individuals with CdLS. ¹³ Individuals with PTHS also have atypical sensory processing. In response to behaviors in social contexts, the majority of individuals are hyporesponsive, but are hyperresponsive to sensory input. ¹³

Stereotypic behaviors are highly prevalent (54%-94%)^{3,6,8,10,12,13} and include object stereotypy,^{3,13} body stereotypies such as body rocking (54%-78%) and hand and finger stereotypies (48-85%) including clapping, flapping (up to 80%), hand-wringing/hand-washing (45%), hand mouthing or biting (54%), finger movements (54%), and wrist movements (45%).^{6-9,12,13} Head shaking and head banging have also been reported.^{6,9}

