### 5.2.5 Post-Baseline Values

For subjects who discontinue the study, data will be analyzed up to the last observation for safety and efficacy measures. Missing data for safety assessments will not be imputed. For efficacy rating scale measures other than the exceptions listed below, if an assessment has been completed but has missing items, missing values shall be imputed as follows:

- If 3 or fewer items are missing, the last observation for that particular data element (e.g., item response) will be carried forward.
- The scoring algorithms will be applied including the observed values and last observation carried forward (LOCF) for the missing items

These rules will only apply to individual items. Total scores, subdomain and subscale scores will not be carried forward. If the assessment is completely missing, items will not be imputed.

These imputation rules do not apply to the CGI-I, Clinical Global Impression Scale – Severity (CGI-S) or Caregiver Impression of Change assessments. If a particular domain is missing for these assessments, the participant will be excluded from the corresponding analysis. These imputation rules also do not apply to the Caregiver Top 3 Concerns assessment. If a concern is missing for this assessment, the average severity will still be calculated from all non-missing concern severity scores.

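### BPI-SF severity has no score for a behaviour that does not occur, so absent behaviours are either merged with mild ones or left blank and the severity score is lost

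*SAP*

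**What the plan says.** SAP Addendum 9.2.10 repeats the scoring text of SAP 9.2.10 and adds one completeness rule for the totals. The frequency items include a code for absence: "The frequency is scored on a 5-point scale, where 0=never/no problem; 1=monthly, 2=weekly, 3=daily, 4=hourly". The severity items, used for self-injury and aggression only, do not: "The severity is scored on a 3-point scale, where 1=mild, 2=moderate, 3=severe". The ranges given are "Self-Injurious Behavior (score ranges from 0 - 32 for frequency and 8 - 24 for severity" and "Aggressive/Destructive Behavior (score ranges from 0 - 40 for frequency and 10 - 30 for severity". On scoring: "The score for each subscale is the sum of the items within that domain". On completeness: "A subscale score will only be calculated if all items in that domain are answered or can be imputed". The addendum also makes each total depend on every contributing domain being present.

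Missing items are sent to SAP 5.2.5, whose rule opens "If 3 or fewer items are missing, the last observation for that particular data element" and carries that response forward. SAP 5.2.4 does not impute missing baseline values. The form is completed only at Visit 3 and at end of treatment (EOT). Protocol 9.5.9.8 describes the same three severity levels. None of these sections says what severity an item takes when its frequency is 0.

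Under 9.2.10 the severity changes are tested by signed rank and plotted. Addendum 9.3.2 lists the total severity score among the linear regression endpoints.

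**The concern.** A severity score summed over a fixed list of behaviours must give some value to those a child does not show. The plan gives none. A behaviour that stops is the clearest improvement the scale could record, and a behaviour that newly appears is a worsening that should be visible. With no zero, the plan can shorten or hide such changes, or make the severity score incalculable for children who never show some of the listed behaviours. What is at stake is the two severity subscales, the severity total, and the tests, plots and regression built on them.

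**Working it through.** **Reproducing the stated ranges.** Items per subscale = frequency maximum / 4.

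- Self-injury: 32 / 4 = 8 items. Severity at 1 to 3 per item gives 8 x 1 = 8 to 8 x 3 = 24, as stated.
- Aggression: 40 / 4 = 10 items. Severity gives 10 x 1 = 10 to 10 x 3 = 30, as stated.
- Implied total severity: 8 + 10 = 18 to 24 + 30 = 54.

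The ranges reproduce exactly, so the missing zero is part of the scoring as written. A child with no self-injury at all cannot score below 8.

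**Case A: absent items are rated 1.** The change for one item whose behaviour stops, compared with a zero code:

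| Severity at baseline | With a zero code | Rated 1 when absent |
|---|---|---|
| 1 | -1 | 0 |
| 2 | -2 | -1 |
| 3 | -3 | -2 |

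Each stopped behaviour is understated by one point. The reverse also holds: a new mild behaviour changes by 1 - 1 = 0 instead of 1 - 0 = 1. Example: a child has three severe self-injury items, all of which stop, and five that never occur. With a zero code the subscale goes from 3 x 3 = 9 to 0, a change of -9. Rated 1, it goes from 9 + 5 = 14 to 8, a change of -6.

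**Case B: absent items are left blank.** One blank at baseline is enough. It is not imputed (5.2.4), the subscale is not calculated, and under the addendum the total goes with it. The child in the example has five blanks at baseline and therefore no severity score.

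Protocol 5.1 gives population figures: "Between 60-71% of individuals demonstrate self-injurious behaviors", and aggression in 40-54%.

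- No aggression: 100 - 54 = 46% to 100 - 40 = 60%. All ten aggression severity items would be blank, so the aggression severity score and the severity total are lost. At 10 participants this is 4.6 to 6 children; at 20, 9.2 to 12.
- No self-injury: 100 - 71 = 29% to 100 - 60 = 40%, losing the self-injury severity score and the total. The overlap with the first group is not given, so the two shares are not added.

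These shares assume that the cited prevalences apply to this sample. They need no assumption about independence between items. They count only children with none of the behaviours; a child with some but not all would also have blanks.

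**Case C: blank at EOT after a complete baseline.** LOCF applies only if every item of the subscale was rated at baseline and 3 or fewer are blank at EOT. The last observation is then the baseline one, so the recorded change for those items is 0. Example: three severe and five mild self-injury items at baseline, 9 + 5 = 14. The three severe ones stop and are left blank. LOCF gives 14 again, a change of 0. A zero code would give 14 to 5, a change of -9. This case is uncommon, because a blank-when-absent form yields a complete baseline only for a child showing every behaviour on the subscale.

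**The case against.** The strongest reply is that the minima of 8 and 10 point to Case A, the mildest. A behaviour never present then scores 1 at both visits, and its change of 0 is correct. A severe behaviour that stops still moves in the right direction. A mild one that stops is still seen in frequency, which is tested separately. The shortening is towards no change, so it does not inflate efficacy. All of this stands on size. It does not supply a rule: the text never says that absent items are rated 1, and absent and mild remain the same score if they are.

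It can also be said that severity given occurrence is a legitimate construct and needs no zero. But a sum over a fixed 8 or 10 items is not conditional on occurrence. Which convention the published instrument uses cannot be settled from these documents, so the fix should be checked against its manual.

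Some stronger readings are tempting and are not supported:

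- A reader might infer that almost no child would have a complete severity form, by multiplying an assumed occurrence rate over all 18 items. The documents give no per-item rates and no basis for independence. A per-item rate above the cited 40-54% for aggression as a whole would contradict that prevalence.
- A reader might treat carrying a severe rating forward unchanged as a typical outcome. Case C shows how narrow its conditions are.
- A reader might say that the child drops out of the efficacy analysis. Only BPI-SF severity would be lost; BPI-SF frequency and the other measures remain.

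**Conclusion.** The point holds. As written, the scoring has no valid severity value for a behaviour that does not occur. If absent items are rated 1, severity change is understated by one point per stopped behaviour, and the stopping or onset of a mild behaviour is invisible. If they are left blank, the severity subscale and total are lost for any child with a blank at baseline. That includes the 46-60% with no aggression, provided the literature prevalences carry over to a sample enrolled with CGI-S of 4 or more.

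The case report form is not among the documents, so which case applies is unknown. A form that did offer a severity of zero would avoid these outcomes but contradict the stated minima, so the SAP would still need correcting.

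The reach is limited. There is no primary efficacy variable (SAP 8.1 and 9.1), tests are descriptive (SAP 5), and the BPI-SF is one of many secondary measures. This is a scoring correction that should be made; it does not threaten the study's main conclusions.

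**What to change.** In Addendum 9.2.10:

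- Derive item severity as 0 whenever item frequency is 0.
- Restate the severity ranges as 0-24 (self-injury), 0-30 (aggression) and 0-54 (total).
- Apply the LOCF and completeness rules only to severity items whose frequency is above 0.
- Say whether the limit of 3 missing items counts frequency and severity responses separately, and whether it applies per form or per subscale; Section 5.2.5 does not.
- Check the convention against the instrument's scoring manual before database lock. If the manual prescribes another, state that one and align the ranges and missing-item rules with it.

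The cost is one derivation line, a few words of SAP text and a check of the manual. Item frequency is already collected, so no new data are needed.

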#### 9.2.12 Gastrointestinal Health Questionnaire Scores

The GIHQ will be completed at all Screening/Baseline period visits (Visits 1, 2, 3), as well as Week 6 (Visit 9), End of Treatment (Week 13, Visit 16), and Follow-up (Visit 17). Each item is scored on its frequency, relevancy, and importance to the caregiver. The Frequency is measured on a 5-point scale where 0=never; 1=almost never; 2=sometimes; 3=often; 4=almost always. The surgery domain records occurrence as 0=No and 1=Yes. The relevancy is scored on a scale from 1 to 4, where 1 is not relevant and 4 is very relevant. The importance is scored on a scale from 1 to 4, where 1 is not important and 4 is very important. Lower frequency scores indicate fewer gastrointestinal problems. For relevancy, higher scores indicate the question is more relevant and for importance, higher scores indicate the question is more important. The total frequency score is the sum of all item frequency scores. Similarly, the total relevancy and total importance scores are the sum of all item relevancy and importance scores, respectively. The items are grouped into 9 subscales. The subscale score is the sum of all items within the subscale, as shown on the CRF. Missing items will be imputed as defined in Section 5.2.5. The subscale scores will only be calculated if all items within the domain are answered or can be imputed. The subscales are as follows:

- General Health/Pain: Items 1 5, frequency score ranges from 0 20, relevancy score ranges from 5 20, importance score ranges from 5 20.
- Eating, Chewing, and Swallowing: Items 1 9, frequency score ranges from 0 36, relevancy score ranges from 9 36, importance score ranges from 9 36.
- Reflux: Items 1 3, frequency score ranges from 0 12, relevancy score ranges from 3 12, importance score ranges from 3 12.
- Gas and Bloating: Items 1 − 5, frequency score ranges from 0 − 20, relevancy score ranges from 5 − 20, importance score ranges from 5 − 20.
- Diarrhea and Constipation: Items 1 6, frequency score ranges from 0 24, relevancy score ranges from 6 24, importance score ranges from 6 24.
- Personality and Mood: Items 1 5, frequency score ranges from 0 20, Relevancy score ranges from 5 – 20, importance score ranges from 5 – 20.
- Medications: Items 1 9, frequency score ranges from 0 36, relevancy score ranges from 9 36, importance score ranges from 9 36.
- Surgery: Items 1 5, frequency score ranges from 0 5, relevancy score ranges from 5 20, importance score ranges from 5 20.
- Parenting: Items 1 8, frequency score ranges from 0 24, relevancy score ranges from 8 24, importance score ranges from 8 24.

Within subject change is the difference between the score at each relevant follow-up visit and the score at baseline. Summary statistics for the change from baseline in the total and each GIHQ domain score will be displayed at all post-baseline visits. Test-retest

reliability will be assessed for all scores collected during the Screening period (Visits 1, 2, and 3, pre-dosing) using ICC. Changes from baseline will be analyzed using a Wilcoxon signed rank test at Week 6 and EOT. The change from baseline in the total frequency score at EOT will be presented in plots as described in Section 9.2. The change from baseline in the domain frequency scores at EOT will be presented in a forest plot (with the exception of the Surgery domain) and waterfall plots. The domain and total frequency scores will be presented in line graphs at each visit, with the exception of the Surgery domain, which is scored differently from the other domains and is not comparable.

#### 9.2.16 Bayley Scales of Infant and Toddler Development version 4

The BSID-4 will be performed at Screening (Visit 1) and End of Treatment (Week 13, Visit 16) on those subjects who cannot be assessed using the SB5. It assesses cognitive ability, motor skills, and behavior and provides standardized scores in five domains: Cognitive (COG), Language (LANG), Motor (MOT), Social-Emotional (SOEM), and Adaptive Behavior. The Adaptive Behavior scale was not collected for this study. Domain scores range from 40 - 160, where higher scores indicate greater ability in the domain area of development. Scaled scores, age equivalents and growth scale values (GSVs) can also be calculated for the scale subtests: cognition (CG), receptive communication (RC), expressive communication (EC), fine motor (FM), and gross motor (GM). Scaled scores and age equivalents can be calculated for the social emotional (SE) subtest. Scale subtest scores range from 1 - 19 with a mean of 10 and SD of 3. Age equivalent scores range from < 0:15 - >41:08, Growth scale scores range from 414 -559 with a mean of 500 and SD of 25. Higher scores indicate greater development in the scale subtest. Raw scores, age equivalent scores and GSV are collected for all subjects. Standard scores and scaled scores are only calculated for participants 42 months and younger.

As part of the analysis, an overall developmental quotient, a verbal developmental quotient, and a non-verbal developmental quotient will also be calculated. These developmental quotients will only be calculated if the contributing scale scores are all non-missing. The developmental quotients will be derived as follows:

**Overall Developmental Quotient:** 

(Mean of the age-equivalent scores in months of the cognition, fine motor, receptive communication, expressive communications scales/chronological age in months) x 100

Verbal Developmental Quotient:

(Mean of the age-equivalent scores in months of the expressive communication and receptive scales/chronological age in months) x 100

Non-verbal Developmental Quotient:

(Mean of the age-equivalent scores in months of the cognition and fine motor scales/chronological age in months) x 100

Subtest/Subdomain Developmental Quotients:

The developmental quotients for the BSID subtests will be derived. The developmental quotients for each subtest are calculated in a similar manner as the overall, non-verbal, and verbal developmental quotients. Subtest Developmental Quotient = (Age Equivalent Score in Months for the subtest / chronological age in months) x 100.

Chronological age in months will be calculated as (date of assessment – date of birth + 1)/30.4375.

For age equivalent values < 2, the result is entered into EDC as 1.9, for analysis. For age equivalent values > X, where X is a numeric value, the result is entered into EDC as X.1, for analysis. For example, ">33" is entered in EDC as 33.1. The age equivalent score entered into EDC will be converted to months for analysis according to the following algorithm:

- (a) Count the numeric portion of the result before the decimal as months.
- (b) Count (the numeric portion of the result after the decimal multiplied by 10) as days and convert to months by dividing by 30.4375
- Age equivalent score (months) = (a) + (b)

The standard scores have a mean of 100 and a standard deviation of 15. The developmental quotient scores are a ratio of developmental age to chronological age and will have a range of 1 to 100. Higher scores indicate a higher IQ or better developmental progress. If any scores are missing, the subject will be excluded from corresponding summaries.

Within subject change is the difference between the score at EOT and the score at baseline. If a score is missing, that subject will be excluded from the corresponding summaries.

Summary statistics for the observed and change from baseline in the age equivalent, growth scale subtest scores, the standard and scale scores (for participants for whom the scores are calculated), and developmental quotients will be displayed at end of treatment. Changes from baseline will be analyzed using a Wilcoxon signed rank test. The change from baseline in the raw scores and GSV at EOT will be presented in plots as described in Section 9.2. The change from baseline in the raw and GSV domain scores will be presented in a forest plot, as described in Section 9.2.

#### 9.2.18 Stanford-Binet Intelligence Scales version 5

The SB5 will be performed at Screening and Visit 16 (End of Treatment). Participants who cannot be assessed on the SB5 due to their developmental level will be assessed using the BSID-4 instead. General cognitive ability is reported as a full scale intellectual quotient score (FSIQ). Cognitive ability in five categories is reported in the index scores: fluid reasoning (FR), knowledge (KN), quantitative reasoning (QR), visual-spatial processing (VS), and working memory (WM). Non-verbal (NVIQ) and verbal intelligence quotients (VIQ) are also recorded. Scores range from 40 to 160, where higher scores indicate a higher IQ. For the analysis of index scores and IQ, the z-deviation method for intellectual disability will be used and z-deviation scores will be derived based on age at assessment according to the published algorithm (Sansone et al. 2014). Standard scores, change-sensitive scores, age equivalents and the raw scores are calculated and entered by the site rater.

For age equivalent values < 2, the result is entered into EDC as 1.9, for analysis. For age equivalent values > x, where X is a numeric value, the result is entered into EDC as X.1, for analysis. For example, ">33" is entered in EDC as 33.1.

Summary statistics on the observed and change from baseline in the z-deviation scores, change-sensitive scores and age equivalents for FSIQ, NVIQ, VIQ. Each category will be displayed at end of treatment. The change from baseline in FSIQ, NVIQ, and VIQ z-deviation scores at EOT will be presented in plots as described in Section 9.2. The change from baseline in the domain z-deviation scores will be presented in a forest plot, as described in Section 9.2.

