The Bayley Scales of Infant Development version 4 (BSID-4) is conducted for participants who cannot achieve a basal score on SB5or for whom the SB5 is developmentally inappropriate. ³⁹ Assessment will be done at Screening (Visit 1) and End of Treatment (Week 13, Visit 16). The Bayley is a norm-referenced developmental assessment validated for ages 16 days to 42 months. It assesses cognitive ability, motor skills, and behavior and provides standardized scores in five domains: Cognitive, Language, Motor, Social-Emotional, and Adaptive Behavior. Scale scores, age equivalents and growth scale values (GSVs) can also be calculated for the scale subtests: cognition (CG), receptive communication (RC), expressive communication (EC), fine motor (FM), and gross motor (GM). Scaled scores and age equivalents can be calculated for the social emotional (SE) subscale. The Adaptive Behavior subscale will not be collected in this study. The Early Learning Composite score and scaled scores are calculated for children 42 months and younger. Raw scores, age equivalents, and growth scale values are calculated for all participants.

If the SB-5 or the Bayley had previously been administered for the participant within 3 months of Screening, the scores from that administration may be used if it meets the following criteria: 1) assessment was administered by site personnel, or another study site; 2) the site has access to all the scores required to be entered in the EDC; 3) the site has permission to share the scores from the previously administered assessment to the study EDC. Assessments done by the school or other clinics

are not acceptable. Only scores from SB-5 and the Bayley are acceptable; cognitive scores from other assessments cannot be entered in the EDC in lieu of the SB-5 or the Bayley.

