## 8.2 Adjustments for Covariates

A list of potential covariates to be used in descriptive summaries or analyses are provided below.

- Age at Baseline
- Sex (Male, Female)
- SB5 NVIQ or BSID-4 NVDQ at Baseline
- History of developmental regression (yes, no)
- ASD diagnosis (yes, no)
- CGI-S Overall Score at Baseline

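### The SAP Addendum's conversion of Bayley-4 age equivalents to months gives wrong values: no reading of it handles both two-digit days and the censoring codes

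*SAP*

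**What the plan says.** Addendum section 9.2.16 describes the scale as follows: "Age equivalent scores range from < 0:15 - >41:08". Two entry rules cover results beyond a limit: "For age equivalent values < 2, the result is entered into EDC as 1.9, for analysis", and "For age equivalent values > X, where X is a numeric value, the result is entered into EDC as X.1, for analysis". Every age equivalent in the EDC is then converted. The part before the decimal is months, and for the part after it the instruction is "Count (the numeric portion of the result after the decimal multiplied by 10) as days and convert to months by dividing by 30.4375". The two pieces are added.

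The section does not say how a value such as 41:08 is typed into the EDC, whether the decimal part is a fraction or a string of digits, or whether the codes 1.9 and X.1 skip the day conversion. Section 9.2.16 of SAP Final Version 1.0 has the same codes but no day conversion. The Addendum also makes derivation of the subtest developmental quotients (DQs) definite, where Version 1.0 made it a fallback.

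The converted values feed the age-equivalent summaries and the overall, verbal, non-verbal and subtest DQs. For these the Addendum says "Changes from baseline will be analyzed using a Wilcoxon signed rank test". The non-verbal DQ is also one of the six candidate covariates in SAP section 8.2 ("SB5 NVIQ or BSID-4 NVDQ at Baseline") and defines the split at 50 in SAP section 9.2.

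**The concern.** The printed limits have day parts of 15 and 08. A multiplier of 10 does not suit a two-digit day field, whether the decimals are taken as a fraction or as whole digits. The censoring codes are a second problem. They are markers, not months and days, yet the conversion applies to every score entered and so treats 1.9 as one month plus some number of days.

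A signed rank test uses the sign and the rank of each change. A conversion that distorts days unevenly can alter both. Because the rule can be read in more than one way, two programmers could each follow it and get different DQs from the same data.

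**Working it through.** **Inputs.** Days per month: k = 30.4375 (Addendum 9.2.16). Scale limits: 0:15 and 41:08 (same section). Codes: 1.9 for results below 2, X.1 for results above X (same section). Ages used for DQ effects: 36 and 204 months, that is 3 and 17 years.

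The colon format is taken as months:days. This is inferred, because the unit is not labelled. The support is that 0:15 cannot be years:months, that the conversion itself speaks of months and days, and that Protocol section 9.5.9.3 describes the instrument as "validated for ages 16 days to 42 months".

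**Correct values.** 0:15 is 15/k = 0.493 months. 41:08 is 41 + 8/k = 41.263 months.

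**The rule under each reading:**

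| Entry | Correct | Fraction × 10 | Integer digits × 10 |
|---|---|---|---|
| 0.15 | 0.493 | 1.5 days: 0.049 | 150 days: 4.928 |
| 41.08 | 41.263 | 0.8 days: 41.026 | 80 days: 43.628 |
| 4.25 | 4.821 | 2.5 days: 4.082 | 250 days: 12.214 |
| 1.9 (code) | below 2 | 9 days: 1.296 | 90 days: 3.957 |
| 33.1 (code) | above 33 | 33.033 | 33.329 |

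- *Fraction reading.* Days shrink ten-fold when entered with two digits. If single-digit days are entered without a leading zero, order can reverse: 12:09 entered as 12.9 gives 9 days, while 12:20 gives 2 days. The codes 1.9 and 33.1 stay on the right side of their limits. If a result above 41:08 is coded 41.1 (an assumption), it becomes 41 + 1/k = 41.033, below its own limit of 41.263.
- *Integer reading.* Days grow ten-fold and order is lost: 4.25 converts to 12.214, above 5.00. The code 1.9 lands at 3.957 months, nearly twice its bound. A ceiling code of 41.1 gives 41 + 10/k = 41.329, which is on the correct side.
- *One digit counting tens of days.* Entries .1 and .2 correctly give 10 and 20 days, and 41.1 again gives 41.329. But 15 or 08 days cannot be entered, and 1.9 again becomes 3.957.

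**Largest error, taking a day part of 30:**

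- Fraction, two-digit entry: 0.9 × 30/k = 0.887 months. As DQ points, 0.887/36 × 100 = 2.5 at 36 months and 0.887/204 × 100 = 0.4 at 204 months.
- Integer: 9 × 30/k = 8.871 months. As DQ points, 24.6 and 4.3.

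**Effect on a change score (constructed examples):**

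- 10:28 to 11:02. Correct: (11 + 2/k) − (10 + 28/k) = +0.15 months. Fraction: (11 + 0.2/k) − (10 + 2.8/k) = +0.91. Integer: (11 + 20/k) − (10 + 280/k) = −7.54.
- Below 2 (coded 1.9) to 3:00, integer or tens reading: 3.00 − 3.957 = −0.96, so an improvement is scored as a decline.

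**Yardstick.** Screening to end of treatment is 17 to 19 weeks, or 119/k = 3.9 to 133/k = 4.4 months. It could reach about 7.4 months where the protocol's allowance for an earlier test applies ("If the SB-5 or the Bayley had previously been administered for the participant within 3 months of Screening"). A 0.89-month error is therefore about 20–23% of the 3.9 to 4.4 months that elapse between tests in the usual case.

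**The case against.** The best defence is that one decimal digit was meant to count tens of days. If uncensored scores come in ten-day steps and trailing zeros drop on storage, the × 10 rule is exact for them. The only day values that the documents print, 15 and 08, belong to the scale's limits, so they do not settle the spacing of ordinary scores. The code for results below 2 may also have been carried over: nearly the same sentence stands in the SB5 section, and the BSID-4 floor is below 0:15, not below 2. If that code never occurs for the BSID-4, its failure has no effect. The integer reading gives such implausible values that the independent programming in SAP section 5 should expose it.

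Part of this stands. The spacing of scores is not documented, the code may be rare, and the largest errors need the integer reading and the youngest children. But ten-day steps are nowhere stated, and the BSID-4 section itself prescribes the code 1.9. Under the tens reading that code still fails. Independent programming would show a disagreement but not which reading is right.

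The outputs are also of limited weight. DQs are not among the efficacy variables in SAP section 8.1, no BSID-4 score is a regression endpoint in section 9.3.2, and all tests are descriptive.

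**Conclusion.** The concern holds. As written, the rule gives wrong months for the day values that the section prints, or for the censoring code that it prescribes, and under the integer reading for both. The size depends on a reading that the Addendum does not state: up to 0.89 months per age equivalent (fraction) or 8.87 months (integer), so the direction of error is unknown. The conclusion rests on the months:days interpretation and, for the maxima, on day parts of up to 30.

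The problem is confined to secondary and descriptive outputs: age equivalents, DQs, the non-verbal DQ as baseline characteristic and covariate, and the split at 50. Raw scores and growth scale values, which are the plotted BSID-4 metrics, are unaffected, and so is the primary safety, tolerability and PK objective. It should be corrected because the rule is specific, wrong and easy to repair.

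**What to change.** In Addendum section 9.2.16:

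1. State how BSID-4 age equivalents are entered in the EDC, including leading and trailing zeros.
2. Define age equivalent in months as months + days/30.4375, with days taken from the source month:day value.
3. Exempt the codes 1.9 and X.1 from the day conversion. Give them a rule that keeps each on the correct side of its limit, including results above 41:08, and say whether the code for results below 2 applies to the BSID-4 at all.
4. Add worked examples, such as 0:15 = 0.493 and 41:08 = 41.263.

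Changing the multiplier to 100 is not enough, because 1.9 would still become 1 + 90/30.4375 = 3.96 months. The cost is one derivation line, one rule for censored results, and a check of EDC entries against source for 10 to 20 participants at two visits.
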